9.3.1 Telephone Follow Up Script

In general, the Day 7, 11, 14, and 180 (±2 days) follow up will be administered over the phone, but may be completed in person. These phone visits are when the primary data will be collected. It is imperative that all visits be completed on a timely and regular fashion.

- 1) *Drink Number:* Make sure the parent/caregiver has the correct drink number as you are completing the Follow-Up Form.
 - a) Ask the parent/caregiver the number on the drink bottles and this should be confirmed with the computer program provided by the data manager.
 - b) If this number is not consistent, the parent/caregiver should be alerted not to give their child any more drinks and the project coordinator should be immediately alerted after completing this week's Follow-Up Form
- 2) Daily Assessment Diary: Ask the parent/caregiver to collect the Daily Assessment Diary for the phone conversation. A lot of the information that will be collected on the Follow-Up Form has been collected by the parent/caregiver on their Daily Assessment Diary. If they have not been using the Daily Assessment Diary, please positively stress the importance of the Daily Assessment Diary.
- 3) Explain to parent/caregiver that we are supposed to fill out this Follow-Up Form today and it should take about 5 minutes.

4) Administer Follow-Up Form.

- When entering sick days, missing school or daycare, etc., this should be generally whole
 integers. However, it is possible that a child missed only 2 hours to go to the doctor. All
 numbers under 4 hours should be counted at 0.5 days, and all those above rounded up
 to next integer.
- The parent/caregiver needs to decide if any activities were missed due to an illness. This is for all illnesses, even those that we are not collecting data about.
- For some questions the RA may say, "Did your child visit a doctor?" A doctor is defined as any medical personnel in this study. Therefore, the parent/caregiver may say, "Never, but s/he saw a nurse practitioner." Please count this the same as seeing the doctor.
- Satisfaction Questions: Please provide the parent/caregiver with the numbers s/he stated the prior time for a comparison.
- Compliance: Please let the parent/caregiver know that we would like them to give their child the drink every day, but regardless, we appreciate their participation.
- Adverse Events: If the parent/caregiver believes any AE occurred, it is imperative that
 the RA immediately fill out an AE Form, and if there are any SAE, alert the PI and project
 coordinator immediately.
- 5) Confirm the date and time for the next visit's call.

All interventions will be completed by week two of the trial. At day 180, participants will be queried for changes in baseline health, onset of new chronic medical conditions and non-routine medical visits in the past 6 months.

Table 8. Participant Timeline and Sample of Data Collection Schedule (N=300)

Study Day	0/1	2	7	10	11	14	21	30	180 ³
Enrollment (baseline health and demographics)	Х								
Antibiotics	→	→	→ or →	→					
Yogurt Interventions	→	→	→	→					
Fecal Sample Collection	Х		Х			Х	Х	Х	
Follow-up Data Collection			Χ		Χ	Х			Х
Daily Assessment Diary ¹	→	→	→	\rightarrow	\rightarrow	→			
16S rRNA Gene Sequences	Х		Х			Х	Х	Х	
Metatranscriptome Analysis ²	Х		Х						
PedsQL™	Х		Х			Х			
Diet Recall Diary (2 x 2 days)		→	→	→	→	→			
Clostridium difficile Analysis ²		→	→	→	→	→			
Adverse Event (AE) Reporting	→	→	→	\rightarrow	\rightarrow	\rightarrow	\rightarrow	\rightarrow	→

¹Participants keep a diary from Days 1 through 14 (collected on Days 7 and 15). Information on stool number, shape and consistency, health, use of interventions, symptomatic care, quality of life, and AEs. ²Will be conducted on all participants with clinically-defined diarrhea.

³Day 180 follow-up is required by the FDA for a safety measurement. On day 180 parents will be asked if they believe there were any additional AEs associated with the yogurt intervention that they have not reported during the previous data collection periods.

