2 PROTOCOL SUMMARY

Title: Efficacy and safety of BB-12 supplemented

strawberry yogurt for healthy children on

antibiotics

Phase: Phase 2

Population: 300 Healthy Children on Antibiotics for a

Respiratory Infection

Number of Sites: Single Center

Study Duration: 60 months

Subject Participation

Duration:

7-10 days of active intervention, follow-up until Day 21, and one final follow-up on Day 180

Description of Agent or

Intervention:

Probiotic, BB-12, supplemented yogurt, 4 ounces taken orally for 7-10 days, concurrently with 7-10

course of antibiotics

Objectives: Primary Objective:

To test the efficacy of *Bifidobacterium animalis* subsp. *lactis* (*B. lactis*) strain BB-12 (BB-12) in preventing diarrhea compared to a control in

children taking antibiotics.

Secondary Objective:

To assess the safety of strawberry flavored yogurt

supplemented with BB-12.

Description of Study

Design:

Randomized, double-blinded, controlled clinical

trial

National Clinical Trial

(NCT) Number:

NCT03181516

Georgetown University Institutional Review

Number:

2016-1489

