4.1.4 BB-12 Survival in Stools

The ability to isolate an orally administered probiotic in the stools is considered to be a good indicator that the strain is able to reach key target sites throughout the intestinal tract. The ability of BB-12 to survive intestinal transit has been documented in several studies.[36-39] Taken together, these studies document the ability of BB-12 to survive gastrointestinal transit and persist for 1-3 weeks post feeding. However, the degree of persistence is likely due to doses fed, delivery vehicle, host factors and the ability of BB-12 to grow during colonization. Studies such as the one proposed here are needed to document the success of probiotic survival in foods supplemented with probiotics.

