II. Safety of BB-12 Supplemented Strawberry Yogurt For Healthy Children: The primary objective of our Phase 1 pediatric study was to assess the safety of strawberry flavored yogurt supplemented with Bifidobacterium animalis subsp. lactis strain BB-12 when consumed daily for 10 consecutive days by generally healthy children. The secondary objective was to assess the ability of BB-12 to survive gastric transit. The participants in the study were healthy individuals between the ages of 1-5 years. Participants were recruited through CAPRICORN. Twenty-nine participants received the BB-12 yogurt and 31 participants received the control yogurt. All reported adverse events were tabulated by type and treatment group (Table 2). Three serious adverse events were reported (details in Table 2). No participant deaths were reported and no participants withdrew from the study due to adverse events.

Both studies, Safety of BB-12 Supplemented Strawberry Yogurt For Healthy Adults on Antibiotics and Safety of BB-12 Supplemented Strawberry Yogurt For Healthy Children were conducted under the same IND.

Table 2. Phase I Pediatric Study Adverse Events

	Days 0-10			Days 11-180		
	(During Intervention)			(Post-Intervention)		
Event	Control	BB-12	Total	Control	BB-12	Total
Allergies (e.g. seasonal)	1	2	3	1	3	4
Broken finger					1	1
Bronchiolitis					1	1
Cold	2		2	2	1	3
Constipation		3	3	2	1	3
Cough	5	10	15	1	5	6
Croup					1	1
Cut finger				1		1
Diarrhea	2	2	4	2	5	7
Ear aches					1	1
Ear infection				2	1	3
Fever		2	2	2	3	5
Flatulence	2	2	4	1	1	2
Headache				1		1
Hives		1	1			
Irritability	4	1	5	3	5	8
Laceration				1		1
Lack of/decreased appetite	2	2	4	3	1	4
Lethargy	1	5	6			
Loose stool	2	6	8	3	3	6
Lump on back of head				1		1
Nasal congestion	4	6	10		2	2
Pain	2	1	3	2		2
Physical injury				1		1
Pink eye					1	1
Pneumonia					1	1
Rash		2	2	1	2	3
Runny nose	6	12	18	6	9	15
Skin infection				1		1
Sore foot					1	1
Sore throat	1	2	3			
Strep throat					1	1
Umbilical hernia	1		1			
Vomiting		2	2	1	2	3
Total	35	61	96	38	52	90
Serious adverse events ^a		1	1		2	2

^a Serious adverse events included: 1) grade 4/potentially life-threatening fever reported on day 2, 2) grade 4/potentially life-threatening bronchiolitis reported at day 180 and 3) grade 4/potentially life-threatening pneumonia reported at day 180. All serious adverse events were unrelated to the interventions and resolved.

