9.3 TELEPHONE FOLLOW-UP

On the first day that the participant drinks the yogurt, parents will schedule a phone call for 30 minutes after the drink is consumed, to ensure any adverse events are recorded. Parents will alert study personnel what time their child will consume the first yogurt and study personnel will call the participant 30 minutes after to ensure that there are no side effects from the yogurt.

These follow-up phone visits will be completed on Days 7, 11, 14 and 180 (±2 days). It is imperative that all visits be completed on a timely and regular fashion.

Generally, the Follow-Up Form will be the only form completed during the phone calls, but at times depending on parent/caregiver's report, there may be another form or two.

The follow up period includes all the time previous to the day of the interview. Any incidents that happen the day of the visit would be captured in the next Follow Up Visit.

There will be a set day that each subsequent visit should be completed for each participant. The research personnel should call all parent/caregiver's phone numbers at least one time per day in order to collect the data. If more than 3 business days have passed from the set day, the RA should alert the PI that this week's Follow-Up Form has not yet been completed. If the RA is not able to contact the participant, a Missed Visit Report Form should be completed instead and the PI should be alerted once again.

If a participant is unmasked at any point in time in during the study, PI will be alerted immediately. A Georgetown University employee in the Department of Family Medicine not associated with the study will follow up with this participant from this point on. This particular research personnel is not to discuss any information regarding this occurrence with any other personnel other than the PI.

Additional stool samples will be collected on Days 7, 14, 21 and 30 (±2 days) (Table 8).

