- 12. Contact the research personnel as soon as possible to arrange a time for stool collection pickup, which should typically occur within 24-48 hours.

Please avoid contact with the liquid preservative in the stool containers. If any of the liquid comes into contact with skin or eyes, wash thoroughly with water. Do not ingest/drink the preservative.

[figure not shown]

Photo B

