10.2 STOPPING CRITERIA

Drink administration may be suspended if:

- Any study participant experiences death that the DSMB believes may be related to the drink administration.
- If statistically or clinically significant amount of hospitalizations occur that the DSMB believes may be related to drink administration.
- New information from outside studies reveals that it would be unethical to continue enrolling participants in the study.
- The IRB decides that the study should be stopped.
- Any serious adverse event for which a relationship with the study product cannot be ruled out.
- The occurrence of statistically or clinically significant, similar Grade 2/moderate adverse events in the study population that the DSMB or PI believe is related to the intervention.
- A statistically or clinically significant number of severe adverse events occur in the study population.

Individuals may be withdrawn from the study for any of the following:

- Adverse events; the PI will discuss AEs with the parent/caregiver, and possibly
 with the participant's physician, as needed, to determine whether the participant
 should be withdrawn from the study.
- If parents/caregivers or participants are deemed to be non-cooperative (e.g. refuse to collect stools, participate in follow-up calls or fail to complete diaries).
- If parent/caregiver is lost to follow-up, i.e. more than 1 week without contact with study personnel during the follow-up period.
- Serious adverse events related to drink administration, as determined by PI, parent/caregiver or participant's primary care physician.

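### No scheduled adverse-event query falls between the Day 14 and Day 180 calls, although the summary and Table 8 imply follow-up to Day 21 or 30 and BB-12 may persist to between Day 14 and Day 31

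*Combined protocol and SAP*

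**What the plan says.** The call schedule is the same in sections 9.3 and 9.3.1 and in Table 8's Follow-up Data Collection row: "In general, the Day 7, 11, 14, and 180 (±2 days) follow up will be administered over the phone". One further call follows the first drink by 30 minutes. The diary, which includes AEs, covers Days 1 to 14 and is collected on Days 7 and 15 (Table 8, footnote 1).

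Other parts of the protocol describe a longer period:

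- The Protocol Summary gives participation as "7-10 days of active intervention, follow-up until Day 21, and one final follow-up on Day 180".
- Table 8's AE Reporting row has arrows on every listed day, including Days 21, 30 and 180.
- Section 4.1.4 says BB-12 can survive transit and "persist for 1-3 weeks post feeding". Its next sentence says the degree of persistence depends on dose, vehicle and host factors.

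Staff already deal with families after Day 14. Section 9.3 states "Additional stool samples will be collected on Days 7, 14, 21 and 30 (±2 days) (Table 8", and section 9.5 tells parents: "Contact the research personnel as soon as possible to arrange a time for stool collection pickup, which should typically occur within 24-48 hours". Sections 9.4 and 9.5 describe these contacts only as sample collection.

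At Day 180, section 9.3.1 asks about changes in baseline health, new chronic conditions and non-routine medical visits over six months. Footnote 3 of Table 8 limits the AE question to further events that parents believe the yogurt caused.

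**The concern.** Safety is the secondary objective, and section 11.3 plans AE rates with 95% confidence intervals and a comparison between groups. That comparison needs events to be sought in the same way in every child over a stated period. Active ascertainment stops at Day 14, which is 4 to 7 days after the last yogurt. By the protocol's own persistence figure, that may be while the organism is still present.

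After Day 14, a new event in a child with no open AE is recorded only if a parent volunteers it, or recalls it months later and attributes it to the yogurt. The likely results are undercounted late events and less sensitivity to a difference between groups. Because the trial is double-blind, under-reporting should be broadly similar in both groups. However, contact after Day 14 is more intense for children with an AE still open, so ascertainment could differ if the groups differ in open AEs at that point.

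The internal disagreement matters whatever one thinks of the design: a reader of the summary or of Table 8 would assume safety follow-up that no form or script delivers.

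**Working it through.** **1. Reproduce the plan's own day count.** Section 11.4.3 says children are followed for 20-23 days after a 7-10-day antibiotic course, to Day 30. 30 − 10 = 20 and 30 − 7 = 23, so this agrees.

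**2. Gap between scheduled calls** (sections 9.3 and 9.3.1).

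- Nominal: 180 − 14 = 166 days, and 166/180 = 92% of the follow-up.
- With the ±2-day windows: 178 − 16 = 162 to 182 − 12 = 170 days.

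Section 9.3 defers events on the day of a call to the next call. The diary covers Day 14 and is collected on Day 15, so the uncovered period is counted from Day 15.

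**3. Overlap with stated persistence.** Inputs: last yogurt on Day 7 to 10 (section 9.2) and persistence of 1 to 3 weeks (section 4.1.4).

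| Last yogurt | Day 14 call, days after last yogurt | 1 week ends | 3 weeks end | Persistence days after Day 14 |
|---|---|---|---|---|
| Day 7 | 14 − 7 = 7 | 7 + 7 = Day 14 | 7 + 21 = Day 28 | 0 to 14 |
| Day 10 | 14 − 10 = 4 | 10 + 7 = Day 17 | 10 + 21 = Day 31 | 3 to 17 |

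Overall, persistence ends between Day 14 and Day 31, and 0 to 17 days of it fall after active ascertainment has stopped. Section 8.2 also speaks of ten consecutive days of yogurt. If every child takes ten days, only the second row applies.

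**4. What reaches a new event after Day 14?**

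- Sections 10 and 10.1: a 24-hour telephone line, AE cards held by families, and reporting open at any time after enrolment. All are passive.
- Sections 10.1.1 and 10.1.2: AEs are monitored to resolution, and expected non-serious AEs open at Day 14 are followed at least every 4 days. This is active, but only for events already known. Unexpected non-serious events judged unrelated or unlikely related are closed at Day 14.
- Day 180: structured health questions with six-month recall, and an AE question restricted by believed cause.

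None is a scheduled query for new AEs in all children on Days 15 to 30.

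**5. If AEs were asked about at the Day 21 and Day 30 stool contacts.** The gaps become 21 − 14 = 7, 30 − 21 = 9 and 180 − 30 = 150 days. Active ascertainment then reaches 20 to 23 days after the last yogurt. Three-week persistence is covered except for Day 31 when yogurt ends on Day 10. If section 9.3's rule that a contact covers only earlier days is applied strictly, Day 30 is missed too.

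**6. Lost-contact criterion.** Section 10.2 treats "more than 1 week without contact with study personnel during the follow-up period" as loss to follow-up. Counting stool contacts, the plan itself has intervals of 9 days (Day 21 to 30) and 150 days (Day 30 to 180). Counting calls alone, it has one of 166 days. All exceed 7 days.

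**The case against.** The strongest reply is that AE collection does not stop at Day 14. Families have cards and a 24-hour line, an AE can be reported at any time, Table 8 keeps reporting open, known AEs are followed on, and the Day 180 question on non-routine visits should bring out a hospitalization. This stands against any reader who infers that AEs on Days 15 to 30 cannot be recorded. It does not answer the narrower point that no one is scheduled to ask.

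Second, section 4.1.4 concerns recovery in stool and does not define a risk window, and persistence varies. This also stands. The lower end of the range is zero days, and reading persistence as a reason to ask about AEs is an inference.

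Three stronger readings are tempting and unsupported:

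- The earlier pediatric study lists "grade 4/potentially life-threatening bronchiolitis reported at day 180" and a pneumonia likewise, both in the BB-12 group. A reader might infer late detection of product-related harm. The same footnote calls all serious events unrelated and resolved, and gives no onset dates. That study's contact schedule is not described.
- A reader might infer that section 10.1's emergency process fails, or count children enrolled before a late report. The immediate alert starts when staff learn of the event, and the teleconference follows only if stopping criteria are thought to be met. A head count would need a serious event just after Day 14, silence from the family until Day 180, and a finding that halts enrolment.
- A reader might infer that compliant children will be withdrawn under section 10.2. The text says only that individuals may be withdrawn, and it is aimed at caregivers who are lost to follow-up.

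**Conclusion.** The point holds as one about scheduled, active ascertainment. For 166 days (162 to 170 with windows) no routine AE query is planned. Between 0 and 17 days of that time fall within the protocol's stated persistence of BB-12, depending on when yogurt ends and whether persistence is nearer one week or three. The schedule also disagrees with the Protocol Summary's Day 21 and with Table 8's AE Reporting row.

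The consequence is weaker evidence on the safety objective and a less sensitive comparison of AE rates. It is not evidence of harm, nor of a failed safety system. The primary outcome, diarrhea within 14 days, is largely unaffected. The mismatch between section 10.2's one-week criterion and the planned gaps is real but separate: the passages conflict as written, and the documents do not show that any child would be withdrawn because of it. The change is worth making because it is cheap and uses contacts that already exist.

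**What to change.** - At the Day 21 and Day 30 stool pick-up contacts, ask the Follow-Up Form's AE item, covering all AEs since the last contact whatever the believed cause. If no stool is provided, ask by telephone, so that ascertainment does not depend on giving a sample.
- Mark Days 21 and 30 in Table 8's Follow-up Data Collection row, and bring the Protocol Summary and sections 9.3 and 9.3.1 into line.
- Reconcile section 10.2's lost-contact criterion with a schedule whose planned gaps exceed one week. Which text gives way is for the sponsor and investigator.

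Cost: a few minutes at each of two existing contacts (section 9.3.1 puts the whole form at about 5 minutes), no added visit, and two more forms per child. Section 13.1 has the Follow-up Form double-entered, so 2 forms × 300 children × 2 entries = 1,200 keyings. The form itself is not in the documents, so the wording of its AE item should be checked before use.

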10.1 ADVERSE EVENTS

An adverse event (AE) refers to any untoward medical occurrence in a clinical investigation subject administered an investigational product and which does not necessarily have a causal relationship with the treatment. An AE can therefore be any unfavorable and unintended sign, symptom, or disease temporally associated with the use of the investigational product, whether or not considered related to the product. This includes events not present at the start of the study or worsening during the course of the study even if present at the study start. An AE can be reported anytime after study enrollment; a participant is considered enrolled once the informed consent form is signed by the parent/caregiver.

Details of all solicited and unsolicited adverse events reported by parents/caregivers or observed by research personnel must be recorded in the adverse event report forms. Parents/caregivers will be provided with cards, which will list the most likely possible adverse events (see **Table 9**), where they can record solicited and other unsolicited events not already listed. All adverse events observed must be recorded separately and all must be reported to the IRB on IRB AE forms. All AEs regardless of severity level will be evaluated by full DSMB during scheduled meetings. The severity of adverse events will be recorded as follows:

- Mild (Grade 1): no or minimal interference with the subject's daily activity with intervention not indicated
- Moderate (Grade 2): some interference with the subject's daily activity but with intervention indicated
- Severe (Grade 3): prevents subject's daily activity and requires medical intervention
- Potentially Life Threatening (Grade 4): ER visit or hospitalization, with intervention indicated to prevent permanent impairment, persistent disability, or death
- Fatal (Grade 5): death

Based on the safety record of the yogurt, we anticipate that the following are the most likely AEs:

 Gl distress including: bloating, flatulence, nausea, emesis, anorexia, constipation and diarrhea • Allergic reactions including: anaphylaxis, hives, shortness of breath, rash, wheezing, and other reactions that the parent/caregiver or doctor believes may be related to food.

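### The Day 180 adverse event question is worded as events the parent links to the yogurt, which is narrower than the protocol's own AE definition, call script and AE analysis

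*Combined protocol and SAP*

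**What the plan says.** **The Day 180 AE question.** Footnote 3 to Table 8 says that at Day 180 "parents will be asked if they believe there were any additional AEs associated with the yogurt intervention", limited to events not already reported.

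**The other Day 180 questions.** The text just above Table 8 has the same contact ask about "changes in baseline health, onset of new chronic medical conditions and non-routine medical visits in the past 6 months". None of these depends on what the parent thinks the cause was.

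**The call script.** Section 9.3.1 applies its script to the Day 7, 11, 14 and 180 calls. Its AE item tells the research assistant to complete an AE form at once if the parent believes any AE occurred, with no condition on relatedness. Section 9.3 adds: "The follow up period includes all the time previous to the day of the interview".

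**The definition and window.** Section 10.1 counts an event as an AE "whether or not considered related to the product", and states: "An AE can be reported anytime after study enrollment". The "Adverse Event (AE) Reporting" row of Table 8 runs through to Day 180.

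**The analysis.** Section 11.3 will estimate AE rates with 95% confidence intervals and compare them between groups. It does not restrict this to related events.

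**The concern.** Safety is Objective 2, and Section 10.1 sends every AE to the DSMB regardless of severity. After Day 14 there is no diary and no follow-up call until Day 180, so scheduled questioning about late events rests on one contact. If staff follow the footnote, the one question there that is framed as AE collection passes through the parent's view of cause. A cold, a fever treated at home or a brief rash could go unmentioned because nobody thought of the yogurt.

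The AE count would then follow one rule up to Day 14 and a narrower one afterwards, while the analysis treats it as a single all-cause measure.

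**Working it through.** No stated figure in the plan depends on this point, so the check is mainly a comparison of texts, followed by an attempt to size the effect.

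**Step 1. Which rule applies to a late event?**

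| Source | Condition on parent's view of cause? |
|---|---|
| Section 10.1, AE definition | No |
| Section 9.3.1, script AE item (covers Day 180) | No |
| Section 9.3.1, health change, chronic condition and visit questions | No, but not stated to feed the AE form |
| Table 8, footnote 3 | Yes |
| Section 11.3, AE rate comparison | No |

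The footnote is the only source that filters on cause.

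**Step 2. Which events can fall through?** An event must (a) start after the last follow-up call, (b) not change baseline health or become a chronic condition, (c) lead to no non-routine visit, (d) not be linked by the parent to the yogurt, and (e) not be volunteered through another channel. That describes minor illness managed at home. An event failing (b) or (c) would probably be mentioned, but the text does not say it becomes an AE record.

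**Step 3. Are such events common?** The only guide is Table 2, the sponsor's Phase 1 pediatric trial, Days 11-180.
- Control 38 + BB-12 52 = 90 events in 31 + 29 = 60 children; 90 / 60 = 1.5 per child.
- Runny nose 15 + irritability 8 + diarrhea 7 + cough 6 + loose stool 6 + fever 5 = 47; 47 / 90 = 52%. These are types that can resolve without a visit. The table does not say how many did.

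**Step 4. Can the loss be computed?** Scaling gives 1.5 × 300 = 450 events. If a fraction c were captured, and the filtered question were the only source, the number unrecorded would be 450 × (1 − c). The values of c are assumptions:

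| c | Unrecorded |
|---|---|
| 0.10 | 405 |
| 0.25 | 337.5 |
| 0.50 | 225 |

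These are not estimates. The documents give no value for c, and the filtered question is not the only source. The 450 includes Days 11-14, which this trial covers by diary and calls. The Phase 1 children were healthy and aged 1-5, whereas these are aged 3-12 and on antibiotics. Nor is the Phase 1 Day 180 question given; had it carried the same filter, the 90 would already be a filtered count.

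**Step 5. What would equal under-recording do to the comparison?** Use the Phase 1 counts as an illustration and treat events as independent Poisson counts, which understates the uncertainty if some children have several.
- Full recording: 52 / 29 = 1.79 and 38 / 31 = 1.23 per child. Difference 0.57, ratio 1.46. SE of log ratio = √(1/52 + 1/38) = 0.213; 95% CI 0.96 to 2.22.
- Half recorded in each arm: 26 / 29 = 0.90 and 19 / 31 = 0.61. Difference 0.28, ratio still 1.46. SE = √(1/26 + 1/19) = 0.302; 95% CI 0.81 to 2.64.

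The absolute difference halves and the interval widens, while the ratio is unchanged.

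**The case against.** The strongest reply is that the footnote is one sentence among several. The same call has three questions free of attribution, and the script covering it tells staff to record any AE. Stool pickups on Days 21 and 30 bring families into contact with staff. Section 10.1.2 follows expected non-serious events unresolved at Day 14 until they resolve, Section 10 provides a 24-hour phone line, and Section 10.1.1 has SAEs evaluated whether or not related. Section 10.1 also describes AEs as temporally associated with the product, so the footnote's wording may be loose shorthand for that. The Day 180 form listed in Section 13.1 is not in the documents, so its actual question cannot be read.

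Much of this stands. It rules out a reading that a reader might take from the footnote alone: that the Day 180 call collects nothing but yogurt-attributed events. Hospitalizations and other events that prompted a non-routine visit would probably come up.

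It does not remove the mismatch. The script item says when to complete a form; it does not give the question that elicits the event. No AE question is scripted at the stool pickups, and the phone line depends on the parent volunteering. Asking what a parent believes to be associated reads more naturally as cause than as timing. Section 13.1 lists the Day 180 form separately from the ordinary follow-up form, so the ordinary form cannot be assumed to govern that call.

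**Conclusion.** The inconsistency is real and worth correcting. Followed as written, footnote 3 can leave unrecorded the minor, self-limited events after Day 14 that parents managed at home and did not link to the yogurt. The route from the other Day 180 answers to the AE record is also unstated.

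Two stronger conclusions might be inferred, and neither is supported. One is that a stated share of late events, such as 50-90%, would be lost: that is only the complement of an assumed 10-50% attribution rate. The other is that the comparison is necessarily biased toward no difference. With blinded arms and equal under-recording, the absolute difference shrinks and precision falls, but the rate ratio need not move. Equal recording across arms is itself an assumption, resting on the blinding.

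This is a moderate point about non-serious late AEs, not a failure to collect late safety data.

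**What to change.** Reconcile footnote 3 with the Section 9.3.1 script and the Section 10.1 definition, and align the Day 180 form:

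- Ask about any new or worsened health problem since the last follow-up call, whether or not the parent thinks the yogurt was involved.
- State that every such problem goes on an AE form, including those that emerge from the health change, chronic condition and medical visit questions.
- Assess relatedness as a separate step after the event is recorded.

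The cost is a reworded footnote and form and a slightly longer call. The downsides are more unrelated background events and recall error over about 5.5 months (Days 15 to 180 are 166 days), which rewording does not cure. Section 11.3 can stay as it is, since its comparison is already all-cause.
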